## **Blinding**

The randomization assignments will not be known to patients. However, due to the nature

Version #: 1.1 Version Date: 08/26/20 Page 10 of 21

of the study, investigators and research staff will need to know the randomization

assignments since investigators will be performing the ablation procedures using devices specific to each randomization group.

#### 9. STUDY PROCEDURES AND GUIDELINES

A Schedule of Events representing the required testing procedures to be performed for the duration of the study is diagrammed in Appendix 1.

Prior to conducting any study-related activities, written informed consent and the Health Insurance Portability and Accountability Act (HIPAA) authorization must be signed and dated by the subject. If appropriate, assent must also be obtained prior to conducting any study-related activities.

#### a. Clinical Assessments

## i. Demographics

Demographic information (date of birth, gender, race) will be recorded at Screening.

## ii. Medical History

Relevant medical history, including history of current disease, other pertinent respiratory history, and information regarding underlying diseases will be recorded at Screening.

#### iii. Adverse Events

Information regarding occurrence of adverse events will be captured throughout the study. Duration (start and stop dates and times), severity/grade, outcome, and treatment will be recorded on the case report form (CRF).

#### 10. EVALUATIONS BY VISIT

## Visit 1: Screening

- 1. Review the study with the subject and obtain informed consent and HIPAA authorization and assent through written paper form or DocuSign.
- 2. Assign the subject a unique screening number.
- 3. Record demographics data.
- 4. Record medical history.
- 5. Record medications subject is currently taking.
- 6. Administer Atrial Fibrillation Effect on QualiTy-of-life questionnaire.
- 7. Ask questions about migraines using CRFs.
- 8. Randomize subject after completion of this visit, 1 day before ablation procedure.

Version #: 1.1 Version Date: 08/26/20 Page 12 of 21

## Visit 2: Ablation Procedure Day

- 1. Ablation procedure performed using assigned randomization group.
- 2. Collect intraoperative data using CRFs.
- 3. Record any adverse events.

## Visit 3: Month 3 (post-study ablation)

- 1. Record any adverse events.
- 2. Record medications subject is currently taking.
- 3. Ask follow-up questions about migraines using CRFs.

## Visit 4: Month 6 (post-study ablation)

- 1. Record medications subject is currently taking.
- 2. Ask follow-up questions about ablation procedure effectiveness using CRFs.
- 3. Administer AFEQT questionnaire.
- 4. Ask follow-up questions about migraines using CRFs.

## Visit 5: Month 12 (post-study ablation)

- 1. Record medications subject is currently taking.
- 2. Ask follow-up questions about ablation procedure effectiveness using CRFs.
- 3. Administer AFEQT Questionnaire.

#### 11. ADVERSE EXPERIENCE REPORTING AND DOCUMENTATION

#### a. Adverse Events

An adverse event (AE) is any untoward medical occurrence in a clinical investigation of a patient. It does not necessarily have a causal relationship with the treatment. An AE is therefore any unfavorable and unintended sign (including an abnormal laboratory finding), symptom, or disease temporally associated with the administration of an investigational product, whether or not related to that investigational product. An unexpected AE is one of a type not identified in nature, severity, or frequency in the current Investigator's Brochure or of greater severity or frequency than expected based on the information in the Investigator's Brochure.

The Investigator will probe, via discussion with the subject, for the occurrence of AEs during each subject visit and record the information in the site's source documents. Adverse events will be recorded in the patient CRF. Adverse events will be described by duration (start and stop dates and times), severity, outcome, treatment and relation to study intervention, or if unrelated, the cause.

Version #: 1.1 Version Date: 08/26/20 Page 13 of 21

## **AE Severity**

The National Cancer Institute's Common Terminology Criteria for Adverse Events (CTCAE) Version 3.0 should be used to assess and grade AE severity, including laboratory abnormalities judged to be clinically significant. The modified criteria can be found in the study manual. If the experience is not covered in the modified criteria, the guidelines shown in Table 1 below should be used to grade severity. It should be pointed out that the term "severe" is a measure of intensity and that a severe AE is not necessarily serious.

Table 1. AE Severity Grading

Severity	Description		
Mild (1)	Transient or mild discomfort; no limitation in activity; no medical intervention or therapy required. The subject may be aware of the sign or symptom but tolerates it reasonably well.		
Moderate (2)	Mild to moderate limitation in activity, no or minimal medical intervention/therapy required.		
Severe (3)	Marked limitation in activity, medical intervention/therapy required, hospitalizations possible.		
Life-threatening (4)	The subject is at risk of death due to the adverse experience as it occurred. This does not refer to an experience that hypothetically might have caused death if it were more severe.		

## b. Serious Adverse Experiences (SAE)

An SAE is defined as any AE that results in any of the following outcomes:

□ death
□ a life-threatening adverse experience
$\ \square$ inpatient hospitalization or prolongation of existing hospitalization
a persistent or significant disability/incapacity
a congenital anomaly/birth defect

Other important medical events may also be considered an SAE when, based on appropriate medical judgment, they jeopardize the subject or require intervention to prevent one of the outcomes listed.

## i. Serious Adverse Experience Reporting

Study sites will document all SAEs that occur (whether or not related to study intervention) per UCSF CHR Guidelines. The collection period for all SAEs will begin after informed consent is obtained and end after procedures for the final study visit have been completed.

Version #: 1.1 Version Date: 08/26/20 Page 14 of 21

In accordance with the standard operating procedures and policies of the local Institutional Review Board (IRB)/Independent Ethics Committee (IEC), the site investigator will report SAEs to the IRB/IEC. All AEs and SAEs will also be reported to Baylis Medical.

## 12.3 Withdrawal of Subjects from the Study

A subject may be withdrawn from the study at any time if the subject or the investigator feels that it is not in the subject's best interest to continue.

All subjects are free to withdraw from participation at any time, for any reason, specified or unspecified, and without prejudice.

Reasonable attempts will be made by the investigator to provide a reason for subject withdrawals. The reason for the subject's withdrawal from the study will be specified in the subject's source documents.

## 12.4 Replacement of Subjects

Subjects who do not undergo the study ablation procedure will be replaced.

#### 12. PROTOCOL VIOLATIONS

A protocol violation occurs when the subject or investigator fails to adhere to significant protocol requirements affecting the inclusion, exclusion, subject safety and primary endpoint criteria. Protocol violations for this study include, but are not limited to, the following:

Failure to meet inclusion/exclusion criteria

Failure to comply with Good Clinical Practice (GCP) guidelines will also result in a protocol violation. The Investigator will determine if a protocol violation will result in withdrawal of a subject.

When a protocol violation occurs, it will be discussed with the investigator and a Protocol Violation Form detailing the violation will be generated. This form will be signed by the Investigator. A copy of the form will be filed in the site's regulatory binder.

#### 13. STATISTICAL METHODS AND CONSIDERATIONS

## a. Data Sets Analyzed

All subjects who undergo a transseptal puncture during their study ablation procedure will be included in the analysis.

#### b. Demographic and Baseline Characteristics

The following demographic variables at screening will be summarized: race, biological sex, gender, age, height and weight.

Version #: 1.1 Version Date: 08/26/20 Page 15 of 21

## c. Analysis of Primary Endpoint

The primary endpoint (transseptal time, in minutes) will be analyzed using a t-test if time is normally distributed and a Wilxocon rank sum test if it exhibits a skewed distribution.

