#### 4. STUDY DESIGN

This is a randomized, single blinded clinical trial comparing transseptal access using the Baylis Versacross RF wire versus the conventional Baylis RF needle among individuals undergoing atrial fibrillation catheter ablation.

Sedation, intubation, vascular access, and catheter ablation will be performed according to usual clinical care. Transseptal puncture will be performed using intracardiac ultrasound guidance. Each patient will undergo two transseptal punctures.

For participants randomized to the RF wire access system, the following equipment will be used:

- o VersaCrossTM RF Wire (Baylis, Montreal, Canada)
- o VersaCrossTM Transseptal Sheath (Baylis, Montreal, Canada)\*
- VersaCrossTM Steerable Sheath (Baylis, Montreal, Canada)\*

For participants randomized to the RF needle, the following equipment will be used:

- o NRG® transseptal needle (Baylis, Montreal, Canada)
- o SL1 sheath (Abbott Medical, Santa Clara, California).
- o Agilis steerable sheath (Abbott Medical, Santa Clara, California)

The primary endpoint is time to complete transseptal puncture. Timing will start when the transseptal sheath wire is inserted into the femoral vein short sheath and will stop when the transseptal dilator is removed from the long sheath after placement in the left atrium. For each transseptal, the number of unsuccessful attempts requiring rewiring will be recorded. Fluoroscopy time, fluoroscopy dose, number of RF applications, procedural complications, and total procedural time will also be determined.

Version #: 1.1 Version Date: 08/26/20 Page 8 of 21

\*Because the transseptal wire does not provide the same mechanical support as a RF needle, these sheaths and their accompanying dilators must be used with the RF wire.

At three months, six months, and one year after the ablation, study coordinators will follow up with participants and ask a series of questions remotely over the phone, or inperson if participants are coming to UCSF for clinical care. Total duration of subject participation will be one year.

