## d. Sample Size and Randomization

The sample size of seventy-two patients will provide 99% power to detect a stastically significant difference in time assuming mean transseptal time of 5 minutes and standard deviation of 5 minutes using a two-tailed alpha of 0.05.

Up to 72 eligible patients will be randomly assigned to either the (1) RF wire group or (2) RF needle group for their transseptal puncture. The randomization codes will be generated prior to the start of enrollment using a computer program to create randomization assignments to either group 1 or group 2, using blocks of 6.

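### Does letting the shape of the data choose between a t-test and a Wilcoxon test leave the primary result open?

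*Combined protocol and SAP*

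**What the plan says.** Section 13.c (Analysis of Primary Endpoint) is a single sentence. It says that the recorded duration "will be analyzed using a t-test if time is normally distributed and a Wilxocon rank sum test if it exhibits a skewed distribution". The rest of the primary analysis is spread over nearby sections. Section 13.a defines the analysis set as everyone who has a transseptal puncture during the study ablation. Section 4 defines when timing starts and stops, and states that "Each patient will undergo two transseptal punctures". Section 13.d sets the level, "using a two-tailed alpha of 0.05", and claims "99% power to detect a stastically significant difference in time assuming mean transseptal time of 5 minutes and standard deviation of 5 minutes" with seventy-two patients. It allocates with a program that will "create randomization assignments to either group 1 or group 2, using blocks of 6".

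No section says how normality is judged, on which data (pooled or by arm), or what happens if the picture is unclear. None names the estimate and confidence interval that go with the test. Section 3 gives only a direction: a shorter time with the RF wire.

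**The concern.** The observed data choose the test, and the rule for choosing is not written down. One analyst might use Shapiro-Wilk in each arm, another a skewness cut-off, a third a histogram. The two tests also address different quantities: a difference in means, or a shift between distributions. The reported benefit therefore depends on the choice as well as the p-value. Section 8 (Blinding) says that investigators and research staff know the assignments, so whoever checks the distribution may know the arms.

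Section 13.d does not clearly settle the matter. A mean of 5 and SD of 5 for the times themselves would imply marked skewness and hence the Wilcoxon test. But the 99% power reproduces only if 5 minutes is the difference between arms, and the arm means are then unstated. At stake would be a primary result whose test and effect measure become known only after the data are seen.

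**Working it through.** **Inputs.** From section 13.d: 72 patients, SD 5 minutes, two-sided alpha 0.05, stated power 99%. Assumed: 1:1 allocation (36 per arm), because the ratio is not stated; lognormal, gamma or normal times; SD 5 in both arms; shorter-arm mean 5, 10 or 15 minutes. The two criteria compared send a trial to the t-test if (a) Shapiro-Wilk p > 0.05 in both arms, or (b) |skewness| < 1 in both arms.

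**Step 1: the plan's own figure.** Take 5 minutes as the between-arm difference.

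- Standard error = 5 × √(2/36) = 1.179.
- 5 / 1.179 = 4.243, and 4.243 − 1.960 = 2.283.
- Power = Φ(2.283) = 98.9%; the noncentral t with 70 degrees of freedom gives 98.7%.

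The 99% reproduces on that reading. For a 2.5-minute difference the t-test has 55% power.

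**Step 2: the literal reading.** If mean 5 and SD 5 describe the times, a normal model puts Φ(−5/5) = 15.9% of them below zero, so the data must be skewed. At that mean, criterion (a) picks the t-test in 0.01% of simulated null trials and criterion (b) in 1% (lognormal) to 4% (gamma). The rule is then a Wilcoxon test in practice.

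**Step 3: type I error.** Across the simulations run, with 5,000 to 20,000 trials per case, the two-stage procedure has size 4.2% to 5.8% under either criterion. Taking whichever test is significant would give about 6% to 7%, but section 13.c does not allow that.

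**Step 4: how often two analysts would differ on significance.** This needs two events in the same trial: the criteria pick different tests, and those tests fall on opposite sides of 0.05. The separate rates peak in different places. The product is a rough guide only. It treats the two events as independent and uses the null rate for the first.

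| Times, shorter-arm mean | Criteria pick different tests (null) | Tests disagree at 2.5 minutes | Product |
|---|---|---|---|
| Lognormal, 5 | 1% | 28% | 0.3% |
| Lognormal, 10 | 15% | 16% | 2.4% |
| Lognormal, 15 | 23% | 11% | 2.5% |
| Gamma, 5 | 4% | 23% | 0.9% |
| Gamma, 10 | 27% | 11% | 3.0% |
| Gamma, 15 | 22% | 8% | 1.8% |

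Simulating the joint event directly for skewed times gives 0% to 0.9% of null trials, 0% to 2.5% with a 2.5-minute difference, and at most 0.3% with a 5-minute difference. For normal times it is below 1% throughout.

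**Step 5: power, and what fixing a test would buy.** Under either criterion, power is within about 1 point of a fixed Wilcoxon test for skewed times and 2 to 3 points above it for normal times. Fixed Wilcoxon against fixed t-test depends on a shape nobody knows in advance:

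| True situation | t-test | Wilcoxon |
|---|---|---|
| Lognormal, means 5 and 3, SD = mean | 59% | 71% |
| Gamma, means 5 and 3, SD = mean | 54% | 45% |
| Normal, 2.5-minute difference, SD 5 | 56% | 53% |

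**The case for a change.** The strongest case for a change rests on the estimate. For mean times of 5 and 3 minutes with SD equal to the mean, the difference in means is 2.0 minutes, while the median pairwise difference (the Hodges-Lehmann target) is 1.22 (lognormal) or 1.11 (gamma). A reader could therefore see a benefit of 2 minutes or of little more than 1, depending on an unwritten choice made by staff who know the arms. Section 14.d also leaves the publication process to agreement between the principal investigator and the device company. A conditional rule is easier to defend when its criterion is written down, and writing one sentence costs almost nothing.

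The facts in this stand: neither criterion nor estimate is stated, and the two estimates differ. But they differ because they measure different things, and each is a valid summary when labelled. Each test has a natural companion, a mean difference for the t-test and a location shift for the Wilcoxon test, and an analyst would report that companion with its interval. Both candidate tests and the condition for each are named in advance, so the discretion is confined to judging skewness.

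Two neighbouring gaps, how the two punctures per patient are combined and whether 5 minutes is an arm mean or a difference, concern definitions and the sample-size text. They do not make the test-selection rule less sound.

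**Conclusion.** The concern describes the text correctly but does not call for a change. Followed as written, with any reasonable mechanical check of skewness, section 13.c gives a test of about the nominal size and with power close to the better-suited single test in most of the cases run. The exception is gamma times with SD proportional to the mean, where the Wilcoxon test that the rule would normally select has 45% power against 54% for the t-test. A fixed Wilcoxon test would share that loss, and a fixed t-test would give up 12 points in the lognormal counterpart. Prespecifying one test is therefore a trade-off, with no clear gain.

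Two good-faith analysts would disagree on significance in fewer than 1% of null trials, in at most about 2.5% at a 2.5-minute difference (a figure chosen for illustration and not in the protocol), and in at most 0.3% at the 5-minute difference behind the stated power. These results assume 36 per arm, SD 5 minutes, the three distribution shapes and the two criteria examined. They also assume that the criterion is applied without regard to which p-value is smaller. What remains is a gap in detail that the analysis report can fill by stating the check used and giving the matching estimate with its 95% confidence interval.

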## d. Sample Size and Randomization

The sample size of seventy-two patients will provide 99% power to detect a stastically significant difference in time assuming mean transseptal time of 5 minutes and standard deviation of 5 minutes using a two-tailed alpha of 0.05.

Up to 72 eligible patients will be randomly assigned to either the (1) RF wire group or (2) RF needle group for their transseptal puncture. The randomization codes will be generated prior to the start of enrollment using a computer program to create randomization assignments to either group 1 or group 2, using blocks of 6.

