#### 2. STUDY RATIONALE

Prior studies have shown that a radiofrequency (RF) transseptal needle is superior to a standard, manual needle with regard to left atrial access time. Recently, a novel RF wire system has been developed to further enhance the speed and safety of transseptal access. With this technique, an atruamatic RF wire can be used to both traverse the fossa ovalis and shield the left atrial wall from traumatic injury secondary to the advancing sheath. While this new RF wire system has recently become clinically available, there is no data substantiating its enhanced efficacy and safety compared to standard needle-based transseptal techniques.

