#### 3. STUDY OBJECTIVES

Primary Objective: To determine if the Baylis Versacross RF wire results in a shorter time to successful transseptal puncture compared to the conventional Baylis RF needle.

Secondary Objectives:

To determine if the Baylis Versacross RF wire results in greater first attempt transseptal puncture success compared to the conventional Baylis RF needle.

To determine if the Baylis Versacross RF wire results in less complications compared to the conventional Baylis RF needle.

Version #: 1.1 Version Date: 08/26/20 Page 7 of 21

To determine if the Baylis Versacross RF wire results in less right atrial needle/wire exchanges compared to the conventional Baylis RF needle.

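### Is the 99% power for 72 patients unsupported because the plan names no between-arm difference?

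*Combined protocol and SAP*

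**What the plan says.** Section 13.d is the only place where the sample size is justified. It claims "99% power to detect a stastically significant difference in time assuming mean transseptal time of 5 minutes and standard deviation of 5 minutes", at a two-sided 5% level. Patients go to one of two groups in blocks of 6; the allocation ratio is not written out.

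Section 13.c covers the primary endpoint, the time in minutes to complete the puncture; it "will be analyzed using a t-test if time is normally distributed and a Wilxocon rank sum test if it exhibits a skewed distribution".

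No other section gives an expected time or time saving. The primary objective in Section 3 is directional only: "To determine if the Baylis Versacross RF wire results in a shorter time to successful transseptal puncture compared to the conventional Baylis RF needle". Section 2 says of the new system that "there is no data substantiating its enhanced efficacy and safety compared to standard needle-based transseptal techniques", which gives no figure for either arm. Section 4 adds that each patient has two punctures, and Section 12.4 that patients who do not have the procedure are replaced.

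**The concern.** The power of a two-sample comparison depends on the difference between arms relative to the spread. A single mean does not determine it. Read literally, Section 13.d gives a location and a spread for one unnamed group and then a power, with the essential input missing.

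Two readings suggest themselves. If 5 minutes is the difference, 72 patients are more than enough. If 5 minutes is the needle-arm mean, a 5-minute saving would put the wire arm at zero, so the true target must be smaller and power might be well below 99%. A mean equal to the SD also points to skewed times: a normal distribution with mean 5 and SD 5 puts Φ(−1) = 16% of times below zero. That makes the Wilcoxon branch of Section 13.c plausible, and its power depends on the shape of the distribution.

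At stake is whether the only stated justification for 72 patients holds, and whether a null result might be over-read on the strength of a quoted 99%.

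**Working it through.** **Inputs.** From Section 13.d: 72 patients, SD 5 minutes, two-sided alpha 0.05, stated power 99%. Assumed: 1:1 allocation (36 per arm), the patient as the unit, and SD 5 in both arms. No dropout allowance is applied, since Section 12.4 replaces patients who do not have the procedure.

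**Reproducing the plan's figure.** Take the difference d as 5 minutes.

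- Standard error of the difference: 5 × √(2/36) = 1.179.
- Standardised difference: 5 / 1.179 = 4.243.
- Normal approximation: Φ(4.243 − 1.960) = Φ(2.283) = 98.9%.
- Exact noncentral t, 70 degrees of freedom: 98.7%.

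Both round to 99%. In the other direction, n per arm for 99% power is 2 × 5² × (1.960 + 2.326)² / 5² = 36.7, so 37 per arm or 74 in total, next to the plan's 72. By the exact t-test, only differences of 4.94 to 5.42 minutes give a power that rounds to 99%.

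**Smaller differences, same t-test.**

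| Difference (min) | Power |
|---|---|
| 2.5 | 55% |
| 3 | 71% |
| 4 | 92% |
| 5 | 98.7% |

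The difference detectable with 80% power is 3.35 minutes, and with 90% power 3.87 minutes.

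**The adverse reading.** Suppose the needle mean is 5 minutes and the wire halves it to 2.5. The 55% above keeps SD at 5 in both arms and assumes normality. That would put Φ(−0.5) = 31% of wire times below zero, so it is not a realistic model of this endpoint. Simulated power for 5 versus 2.5 minutes, 36 per arm, with other shapes (all assumed, since the documents give none):

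| Assumed shape | Wilcoxon | Welch t |
|---|---|---|
| Lognormal, SD equal to the mean | 0.93 | 0.84 |
| Lognormal, SD 5 in both arms | 0.99 | 0.70 |
| Exponential | 0.69 | 0.79 |
| Normal, SDs 5 and 2.5 | not run | 0.75 |

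So the same halving gives anything from about 55% to 99%.

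**Another unit.** Treating the 144 punctures as independent (72 per arm) would give 99% power at about 3.6 minutes. Section 13.d counts patients, and two punctures in one patient are correlated, so this is not a natural account of the calculation.

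**The case for a change.** The strongest case for acting is that this one sentence carries the whole sample size, and a reader cannot tell from it what time saving the trial was built to detect. By the common-SD t-test, a 5-minute difference needs 34 patients for 80% power and 46 for 90%, while a 2.5-minute difference needs 128 and 172. If the second were the real target, 72 would be short and the quoted 99% would mislead. Rewording costs a sentence or two.

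Part of this stands. The difference is not written down, the mean belongs to no arm, and neither the text nor a blackout explains the gap. The identification of 5 minutes as the difference is also an inference that holds for the t-test: a Wilcoxon test on suitably skewed times could reach 99% at a smaller difference.

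The harm does not stand. The 2.5-minute target appears nowhere in the plan, and by the patient-level t-test it does not reproduce the stated 99%, whereas 5 minutes does. The totals of 128 and 172 come from a model that the skew argument itself rejects; under some skewed shapes, a test that the plan names has power above 90% for the same halving. As for over-reading a null result, that is judged from the estimated difference and its uncertainty, which the wording of the planned power does not affect.

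**Conclusion.** The 99% is not a wrong number. It is reproduced at 98.7% by a patient-level two-sample t-test with 36 per arm, a common SD of 5 minutes, two-sided alpha 0.05 and a difference of 5 minutes. The simplest explanation is that the intended difference was labelled as a mean time. That is a slip in reporting an input, and a statistician can recover the input from the other figures in the same sentence.

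Nothing downstream depends on the label. The 72 patients, the randomisation, the endpoint, the choice of test in Section 13.c and the alpha all stay as they are, and the wording of a power statement cannot bias the estimate or the p-value. Whoever reports the trial can state the assumed difference and arm means alongside the sample size.

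The conclusion assumes 1:1 allocation, the patient as the unit and a common SD of 5. The documents do not show whether a 5-minute saving was realistic. For savings below 5 minutes, the t-test figures of 3.35 minutes (80% power) and 3.87 minutes (90%) show what 72 patients can detect.
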